5.9 Safety Monitoring Plan

Study staff will monitor for adverse events and protocol deviations through the end of the study. The PI and study physician (if necessary) will be notified of adverse events shortly after their discovery. If a subject has an adverse event while on site, study staff will help get the care the subject needs. This may include first aid, emergency care, and/or follow-up care.

Adverse events and protocol deviations will be recorded on an Excel spreadsheet that is filed with the IRB at specific intervals. Any “unexpected problems involving risks to subjects or others” (UPIRTSO) will be reported to the IRB within 24 hours of discovery.

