3.1 Study Visits

Visit 1: subjects will come to the UAMS TRI for informed consent discussion. Once consent is obtained, subsequent study procedures will be performed. A medical history questionnaire including allergies and list of current medications will be completed. Females of child bearing capacity will be asked to provide a urine sample for pregnancy testing. About 4mL of venous blood will be drawn to send for complete blood count for study criteria. Blood and urine samples will be sent to LabCorp.

Subjects will be asked to perform the following tests and measurements at visit 1:

Standing height without shoes (in cm),

Body weight without shoes (in kg),

If subject meets the requirements (fasted for at least 8 hours, caffeine-free for at least 12 hours, and did not perform strenuous exercise during the past 24 hours) to perform the DEXA scan and In Body scan on visit 1, these tests will be performed at that time. If they do not, these tests will be performed at Visit 2.

Run-in meals will be discussed with subjects to elicit food allergies or intolerances.

Visit 2: Subjects return to the UAMS TRI. If they will undergo the DEXA and InBody scans, the must have fasted for at least 8 hours, avoided caffeine for at least 12 hours, and avoided strenuous exercise during the past 24 hours. They will be asked about any adverse events since last visit. The In Body, DEXA, ultrasound scans will be performed if these were not done at visit 1. Two days' of run-in meals will be dispensed with instructions on their preparation. Meals will be consumed for the two days immediately preceding Visit 3.

Visit 3: Subjects return to the UAMS TRI having fasted overnight. Study staff will ask about adverse events since their last visit. Vital signs (heartrate, blood pressure and oral temperature) will be measured. The study nurse will insert an IV catheter into a vein of one of the subjects' arms to use for periodic blood sampling, warming the arm by means of a heating pad or a heated plastic box. A second IV catheter will be placed into a vein on of the subject's other arm to use for stable isotope infusion.

After an initial blood sample is obtained, the priming dose of isotopes are given IV push, the constant infusions are begun, and a timer is started. Blood and muscle samples are obtained according to the schedule below.

The study food is served after the 4:00 blood/muscle sample are obtained. Subjects are asked to consume the study food within 10 minutes.

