At the conclusion of 10 hours elapsed time, the IV catheters are removed and the sites dressed with a bandage. Vital signs (heartrate, blood pressure and oral temperature) will be measured. A snack and beverage will be offered to the subject. Subject will then be free to leave.

Elapsed time (min., approximate)	Procedure
-0	Blood sample (~4mL into an EDTA tube)
120	Blood sample (~4mL into an EDTA tube), ingest study supplement, muscle sample from vastus lateralis
150	Blood sample (~4mL into an EDTA tube)
180	Blood sample (~4mL into an EDTA tube)

210	Blood sample (~4mL into an EDTA tube)
240	Blood sample (~4mL into an EDTA tube), muscle sample from vastus lateralis serve study food
270	Blood sample (~4mL into an EDTA tube)
300	Blood sample (~4mL into an EDTA tube)
330	Blood sample (~4mL into an EDTA tube)
360	Blood sample (~4mL into an EDTA tube)
390	Blood sample (~4mL into an EDTA tube)
420	Blood sample (~4mL into an EDTA tube)
450	Blood sample (~4mL into an EDTA tube)
480	Blood sample (~4mL into an EDTA tube)
510	Blood sample (~4mL into an EDTA tube)
540	Blood sample (~4mL into an EDTA tube)
570	Blood sample (~4mL into an EDTA tube)
600	Blood sample (~4mL into an EDTA tube), muscle sample from vastus lateralis

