3.3 Recruitment

Potential subjects will be recruited from the Little Rock and central Arkansas areas by use of UAMSHealth social media, word of mouth, the ARResearch.org registry, and contacting prior subjects who indicated they wanted to be contacted about future studies. UAMS students and employees will not be targeted for participation but will not be refused. Study staff will ask enrolled subjects to recruit others if they are comfortable doing so, and study staff will seek subjects within their social circles. Individuals interested in the study will be scheduled for Visit 1.

Facebook Script:

The Center for Translational Research in Aging and Longevity at UAMS is recruiting healthy individuals ages 18-40 for a study about measuring how blood and muscle proteins respond to either a beef patty or vegi-burger(s).

Participants will be compensated for their time. If interested, please contact us:
Email [contact] or call [contact] for more information.

Twitter Script:

Our research team is recruiting individuals ages 18-40 for a study about how blood and muscle proteins respond to a beef patty vs vegi-burger.

Participants will be compensated! Contact us for more info: email [contact], or call [contact]

During the initial conversation (in person or via phone), the following items will be discussed in non-technical language:

- this study is completely voluntary.
- the goal of the study: to see if beef or vege-burgers are more efficient at making proteins in our body.
- the number of visits to UAMS study site and their duration: 2 visits that are less than an hour, and 1 visit that lasts a bit over 10 hours.
- study procedures: must have 2 IV catheters placed and undergo 3 muscle biopsies from one incision on their outer thigh, eat our food for almost 3 full days, fast overnight twice,

have an x-ray for body composition, must get an infusion of stable isotopes (and define what they are).

- risks of procedures: pain, bruising, bleeding, infection, possible fever/chills, discomfort from fasting, small amount of radiation from x-ray, amount of blood taken (approx.. 5 tablespoons), skin numbness and scar formation from biopsy incision.
- compensation for time and travel: up to \$340 if all 3 visits are completed.

ARRResearch.org:

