L-[ring- ² H ₅] phenylalanine	L-[ring- ² H ₅] phenylalanine
U- ¹³ C ₉ - ¹⁵ N-tyrosine	U- ¹³ C ₉ - ¹⁵ N-tyrosine
L-[ring- ² H ₄] tyrosine	

5.5 Confidentiality:

A potential risk is the loss of confidentiality. Measures to protect the confidentiality of study participants will be implemented as described in the Data Handling and Record keeping section below.

5.6 Intravenous Catheter insertion:

The risks of inserting an IV catheter are pain, bruising, bleeding, and infection.

5.7 Muscle Biopsy:

The risks of the muscle biopsy procedure include pain, bleeding, bruising, infection, residual numbness from the incision, scar formation, soreness lasting >48 hours, and hematoma.

5.8 Covid-19 Related risks:

Subjects will be COVID-19 negative and/or asymptomatic. Subjects will undergo the current screening procedures in place for UAMS patients at the time of their visits. Visitors will not be permitted unless UAMS policy changes permit them. Subjects will be required to wear a suitable facemask for the entirety of their study visits except when ingesting their meals. Study staff will wear their mandated masks and use universal blood-borne precautions while handling blood samples. Study visit areas are disinfected after study visits as per protocol.

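### No staff-initiated adverse event enquiry is scheduled after the infusion and the three biopsies, so delayed harms listed in Section 5.7 reach the log only if the subject calls

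*Combined protocol and SAP*

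**What the plan says.** Section 3.1 places the first adverse event question at Visit 2: "They will be asked about any adverse events since last visit". The second is on arrival at Visit 3, ahead of the catheters: "Study staff will ask about adverse events since their last visit". Each looks back to the preceding visit.

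The recruitment talking points in Section 3.3 describe the whole participation as "2 visits that are less than an hour, and 1 visit that lasts a bit over 10 hours", so Visit 3, the infusion and biopsy day, is the last visit. Its close is set out in Section 3.1: "At the conclusion of 10 hours elapsed time, the IV catheters are removed and the sites dressed with a bandage". Then: "Vital signs (heartrate, blood pressure and oral temperature) will be measured. A snack and beverage will be offered to the subject". Then: "Subject will then be free to leave". No adverse event question appears in that sequence, and no later visit, call or message with a safety purpose is described.

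Section 5.7 lists the biopsy risks. Besides pain, bleeding and bruising they include infection, residual numbness, scarring, "soreness lasting >48 hours, and hematoma". Section 3.7 gives subjects spoken and written wound-care instructions and the study nurse's telephone number.

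Section 5.9 states the general commitment: "Study staff will monitor for adverse events and protocol deviations through the end of the study". It covers care for events that happen on site, notification of the principal investigator, a spreadsheet filed with the IRB, and a 24-hour report of unexpected problems, counted from discovery.

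**The concern.** Section 5.9 makes a commitment that the visit schedule does not fully carry out. Both scheduled questions look back over periods in which nothing more invasive than a screening blood draw and body-composition scans has taken place. The procedures that carry most of the listed risk come after the last question.

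At least one harm that the protocol itself expects, soreness beyond 48 hours, cannot be observed during a 10-hour visit. As scheduled, it enters the log only if the subject chooses to call. A subject who has been told to expect soreness or numbness may see no reason to do so. The lack of a recorded delayed event would then be weak evidence that none occurred.

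This matters for two reasons. The subjects are healthy volunteers with no direct benefit (Section 5.0), and the spreadsheet is what the IRB sees. The notification and 24-hour reporting duties also start at discovery, and no scheduled step after discharge would lead to discovery. A recurring wound problem in early subjects could be noticed late, while later subjects are being studied.

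**Working it through.** The plan states no figure on this point to reproduce. The check sets the order of events against the enquiries and adds simple timing arithmetic.

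**Inputs**
- Biopsies at about 120, 240 and 600 minutes after the start of infusion (schedule table, Section 3.1).
- End of Visit 3 at about 600 minutes (Section 3.1).
- Three biopsies per subject through one incision (Section 3.7).
- Up to 28 enrolled, with a goal of 8 completers in each of three groups, so 24 (Section 4.0).
- Soreness beyond 48 hours as a listed risk (Section 5.7).

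**Step 1. Order of enquiry and procedure**

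| Event | Relation to infusion and biopsies | Adverse event question scheduled? |
|---|---|---|
| Visit 2 | before | yes |
| Arrival at Visit 3 | before | yes |
| Infusion and biopsies, 0 to 600 min | during | no (staff present, on-site care under Section 5.9) |
| Close of Visit 3 | at the end | no (vital signs only) |
| After Visit 3 | after | no (nurse's number given to the subject) |

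Of the two scheduled questions, 0 follow the start of infusion or any biopsy.

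**Step 2. Planned observation after each biopsy**

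Hours observed = (600 − biopsy time in minutes) / 60.
- First biopsy: (600 − 120) / 60 = 8 h.
- Second biopsy: (600 − 240) / 60 = 6 h.
- Third biopsy: (600 − 600) / 60 = about 0 h.

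**Step 3. Comparison with the 48-hour harm**

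Soreness beyond 48 hours can be established no earlier than 48 minus the hours already observed, counted from discharge: 48 − 8 = 40 h for the first biopsy, 48 − 6 = 42 h for the second and 48 − 0 = 48 h for the third. All three fall after the last planned contact about safety.

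**Step 4. Extent**
- At the enrolment ceiling: 28 × 3 = 84 biopsies.
- At the completion goal: 24 × 3 = 72 biopsies.

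None is followed by a scheduled enquiry. The documents give no rate for delayed events and none for spontaneous reporting, so the number of missed events cannot be estimated from them.

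**Step 5. Other contact after discharge**

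The only outgoing item described is the compensation check, mailed about 3 to 4 weeks after participation ceases (Section 3.2). It carries no safety question.

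**The case against.** The strongest reply is that Section 5.9 already promises monitoring to the end of the study and that Section 3.7 provides a planned route for reports after discharge. Both statements are accurate, and they limit the point. They do not remove it, because Section 5.9 names no contact, method or time after Visit 3, and the telephone number depends on the subject to act.

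A reader might infer more than the documents support:

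- *That the invasive day has essentially no safety ascertainment.* Staff are with the subject for about 10 hours, Section 5.9 covers on-site events, and vital signs including temperature are taken before the infusion and again at the close. Fever or chills during the infusion would be observable. The gap concerns delayed events.
- *That monitoring of a subject stops at discharge.* No section says so. Section 5.9 leaves the end undefined, and a report telephoned in later could well be logged.
- *That infection, hematoma and numbness can only appear later.* The documents give no onset times for these. A hematoma could be seen within the 6 to 8 hours after the earlier biopsies. Only soreness beyond 48 hours is late by its own definition.
- *That delayed harms cannot be captured at all.* They can be, if the subject calls.

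It can also be said that Section 7.1 contains no safety endpoint, so no efficacy conclusion depends on this. That is correct. The point is about subject protection and the value of the adverse event log. Finally, the consent pages were removed from the text reviewed and might describe a follow-up contact. If they do, Sections 3.1 and 5.9 should say the same.

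**Conclusion.** The point holds in a limited form. As scheduled, neither of the two adverse event questions follows the infusion or any of up to 84 biopsies, and planned observation after the biopsies is about 8, 6 and 0 hours against a listed harm defined by more than 48. Delayed events therefore depend on subject-initiated calls. The log could understate them, but the documents do not allow that shortfall to be quantified.

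This rests on three assumptions: the nominal times in the Section 3.1 table are followed, Section 3.1 lists all planned contacts, and no further contact is described only in the removed consent pages. The protocol should be changed, because a small addition closes a real safety gap. The primary analysis is unaffected.

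**What to change.** Amend Sections 3.1 and 5.9 as follows:

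1. Add an adverse event question at Visit 3 discharge, alongside the closing vital signs.
2. Add one scheduled study-nurse call or e-mail after Visit 3 that asks the same question. The study physician should set its timing so that it can capture the delayed harms listed in Section 5.7.
3. Record both answers, including negative ones, in the existing adverse event spreadsheet.
4. State what the end of the study means for adverse event monitoring of a subject, and that events reported after the scheduled contact are still logged through the end of the study. Without this, a fixed contact could be taken as the cut-off and shorten the present commitment.

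If the consent form already describes such a contact, copy it into both sections so that the documents agree.

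The cost is one short contact per subject, at most 28, by existing staff, one added question at discharge, and a minor amendment. No new procedure or sample is needed.

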6.0 Data Handling and Recordkeeping

Source documents, paper questionnaires and consent forms, and CRFs will be stored in a secure area of the PI's laboratory. Access will be limited to study personnel. Documents containing identifiers will be destroyed by shredding approximately 7 years after data analysis is completed or publication of data; whichever is longest. At no time shall Protected Health Information be released to non-study personnel.

The Principal Investigator will carefully monitor study procedures to protect the safety of research subjects, the quality of the data and the integrity of the study. All study subject material will be assigned a unique identifying code or number. The key to the code (the instrument associating the data with subject identity) will be kept on a password-protected UAMS server, located behind locked doors in a restricted access area of the UAMS campus. The code file will contain subject initials, sex, subject ID, enrollment data, and anthropometric data; it will not include any identifiers. Only those individuals listed on the title page of this protocol and their research staff members will have access to the code and information that identifies the subject in this study. This file will be deleted approximately 7 years after data analysis is completed.

7.0 Data Analysis

7.1 Statistical Analysis plan

The post-prandial change in net protein balance (i.e., protein synthesis minus protein breakdown) relative to the baseline in each group will be the primary outcome. Responses of the rates of protein synthesis and breakdown will be secondary outcomes. Additional secondary endpoints will be muscle protein synthesis, plasma EAA and insulin area under the curve above baseline values, and protein kinetics normalized by caloric and EAA intake. Correlation analysis of the relation between protein kinetics and the EAA content of the protein food source will be additional secondary endpoints.

One-way ANCOVA will be used to compare differences in protein kinetics (FSR, NB, PS, and PB) and protein kinetics normalized by caloric and EAA intake. Plasma EAAs and insulin area

under the curve above fasting values will be assessed by a one-way ANOVA. All significant main effects of group will be followed with Bonferroni-adjusted pairwise comparisons. Partial Pearson's correlation coefficients controlling for protein source (beef patty or Impossible Burger) will be used for the correlation analysis. Statistical significance will be accepted at $p < 0.05$.

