2.0 Hypotheses

1. Consumption of a 4 oz beef patty will result in a greater anabolic response than consumption of a 4 oz Impossible Burger, including greater increases in plasma EAA

concentrations, a greater balance between whole body protein synthesis and breakdown, and a greater increase in muscle protein fractional synthetic rate (FSR).

2. Consumption of a 4 oz beef patty will result in a greater anabolic response than consumption of two 4 oz Impossible Burgers, including greater increases in plasma EAA concentrations, greater balance between whole body protein synthesis and breakdown, and greater increase in muscle protein FSR.

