4.1 Inclusion Criteria

- Ages 18 – 40 yrs.
- Body Mass Index of 20-32 inclusive.

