5.0 Risks and Benefits

There are no direct benefits for the subjects. Expected risks associated with this protocol are described in detail below. All experimental procedures will be performed by appropriately trained and credentialed personnel.

5.1 Blood sampling:

Blood samples will be collected solely for the purpose of experimentation. The blood will be used to measure plasma amino acid concentrations, stable isotope enrichment, glucose, and insulin. The total amount of blood taken will be approximately 72 mL (~5 tablespoons).

Subjects should have no noticeable effects from this volume.

5.2 DEXA, In Body, ultrasound scans:

The DEXA scan exposes subjects to approximately ½ of the radiation of one chest x-ray.

Subjects will undergo 1 DEXA scan. The In Body and ultrasound scans do not pose any risks.

5.3 Study foods:

The run-in meals are comprised of frozen, ready-to-eat portions that are commercially available at most grocery stores (e.g. Stouffers). The 'test' foods are:

- one 4 ounce (cooked weight) patty of 80/20 beef (from Kroger e.g.)
- one 4 ounce Impossible Burger (<https://impossiblefoods.com/products/burger>)
- two 4 ounce Impossible Burgers

The risk of eating any of these foods is that of a food allergy. Subjects will be shown the list of foods and asked if any of them are intolerable.

5.4 Stable Isotope Infusion:

The primary risks of infusion of the stable isotopes are fever, chills, infection (from contamination). A 0.2 micron in-line filter will be used during the infusion. The isotopes will be purchased from Cambridge Isotope Laboratories (Tewksbury, MA, USA) and sent to the Center for Translational Research in Aging and Longevity at Texas A&M University (College Station, TX) for contractual compounding. Finished products will be shipped to the UAMS Research pharmacist who will store and dispense the isotopes to study staff as needed. Isotopes will be stored in glass vials and frozen until use. Two solutions will be produced: a mixture of L-[ring-²H₅] phenylalanine + U-¹³C₉-¹⁵N tyrosine (for constant infusion IVPB), and a mixture of L-[ring-²H₅] phenylalanine + U-¹³C₉-¹⁵N tyrosine + L-[ring-²H₄] tyrosine (for priming doses IVP).

Isotope rates of infusion:

- L-[ring-²H₅] phenylalanine: priming dose: 3.6µmol/kg. Constant infusion: 3.6 µmol/kg/hour.
- U-¹³C₉-¹⁵N-tyrosine: priming dose: 0.113µmol/kg. Constant infusion: 0.113µmol/kg/hour.
- L-[ring-²H₄] tyrosine: priming dose: 0.31µmol/kg.

IVP vials contain:	IVPB vials contain:

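### Plasma EAA AUC is compared by a valid but unadjusted one-way ANOVA, although the portion is fixed and sex and body size are known before the meal; prespecified adjustment would gain precision at almost no cost

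*Combined protocol and SAP*

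**What the plan says.** Section 7.1 lists the endpoint as secondary: "Additional secondary endpoints will be muscle protein synthesis, plasma EAA and insulin area under the curve above baseline values". It then uses two models. For the kinetics, "One-way ANCOVA will be used to compare differences in protein kinetics (FSR, NB, PS, and PB", together with the versions normalized by calories and EAA intake. For plasma EAA and insulin, the area "under the curve above fasting values will be assessed by a one-way ANOVA". No covariate is named for the AUCs. The only covariate described anywhere is the baseline measure in Section 7.2, which belongs to the primary-outcome ANCOVA.

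Other sections bear on this:

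- Section 2.0 makes "greater increases in plasma EAA concentrations" part of the anabolic response in both hypotheses.
- Section 5.3 fixes the portions, for example "one 4 ounce (cooked weight) patty of 80/20 beef" and "two 4 ounce Impossible Burgers". Nothing scales them to the subject.
- Section 4.1 admits "Body Mass Index of 20-32 inclusive", and Section 3.0 admits both sexes.
- Section 3.1 records body weight at Visit 1 and places the DEXA scan at Visit 1 or 2, before the Visit 3 meal. Section 5.2 confirms: "Subjects will undergo 1 DEXA scan".
- Section 3.6 stratifies the randomization by sex.

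No section uses sex, weight or a DEXA result in a statistical model.

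**The concern.** Plasma EAA AUC is a concentration measure taken after a dose that is the same for a small and a large subject. It is reasonable to expect a smaller rise in a larger body. The documents do not say so, and this remains an inference. Eligibility leaves room for a wide spread of size: at one height, BMI 20 to 32 is a 32/20 = 1.6-fold range of weight. That is the extreme the criteria allow, not an estimate of the spread in the sample.

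An ANOVA with group as its only factor counts all variation due to sex and size as error. Stratifying by sex balances the arms on sex, but it does not remove variance due to sex from the error term of a model that omits it. With 8 completers per arm there is little precision to spare, and the endpoint supports a named component of H1 and H2. What is at stake is power and interval width for plasma EAA AUC. The primary outcome is not affected.

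**Working it through.** **Inputs from the documents.** Three groups of 8 completers, so N = 24 (Sections 3.6 and 4.0); α = 0.05, f = 0.484, 80% power and a baseline covariate explaining 50% of the variance (Section 7.2). Section 7.2 concerns the primary outcome, and no power or effect size is given for EAA AUC. Here f = 0.484 is only a common yardstick.

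**Assumed.** R², the share of within-group EAA AUC variance that the covariates remove. The documents give no value, so a range is shown.

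**Formula.** Omnibus F test with df1 = 2, df2 = 24 − 3 − (number of covariates) and noncentrality λ = N f² / (1 − R²). Power is the probability that a noncentral F exceeds the 5% critical value.

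**Step 1: reproduce the plan's figure.** λ = 24 × 0.484² / (1 − 0.50) = 5.622 / 0.50 = 11.24, with df2 = 20. Power is 80.0% and the smallest f detectable at 80% power is 0.484. The stated figure reproduces.

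**Step 2: the planned ANOVA for EAA AUC.** R² = 0, df2 = 21, λ = 5.62. Power at f = 0.484 is 49%, and the smallest f detectable at 80% power is 0.682.

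**Step 3: add covariates.**

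| Assumed R² | λ | Power, one covariate (df2 = 20) | Detectable f, one | Power, two covariates (df2 = 19) | Detectable f, two |
|---|---|---|---|---|---|
| 0 | 5.62 | 49.0% | 0.684 | 48.6% | 0.687 |
| 0.1 | 6.25 | 53.4% | 0.649 | 53.1% | 0.652 |
| 0.2 | 7.03 | 58.7% | 0.612 | 58.3% | 0.615 |
| 0.3 | 8.03 | 64.9% | 0.572 | 64.5% | 0.575 |
| 0.5 | 11.24 | 80.0% | 0.484 | 79.7% | 0.486 |

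Power is at f = 0.484; detectable f is at 80% power. For two covariates, R² is their joint value.

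**Step 4: break-even.** At the effect the ANOVA detects with 80% power (f = 0.682), one covariate restores that power once R² reaches about 0.7%, and two once joint R² reaches about 1.6%. If the covariates explain nothing, power at f = 0.484 falls only from 49.3% to 48.6%.

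**Step 5: validity of the unadjusted test.** In 40,000 simulated null trials per setting, with three groups of 8 and an omitted covariate explaining 0, 30% or 50% of the variance, the ANOVA rejected in 4.9% to 5.0%. These simulations let the covariate vary freely between arms. Stratifying on a prognostic factor and then omitting it would, if anything, push the rate below 5%.

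**The case against.** The strongest reply is that nothing is wrong. Allocation is randomized, the ANOVA is unbiased with the correct error rate, the endpoint is secondary, and the AUC already has the fasting value subtracted. The ANCOVA for the kinetics is no precedent for adjusting on body size either, since its covariate is the baseline measure. All of this stands. It limits the point to precision, but it gives no reason to leave recorded pre-meal information unused.

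A second reply is that the gain rests on an unknown R². That also stands, so no single gain can be claimed. If the size effect is proportional to dose, its slope would differ between the 4.2 g arm and the 8.4 and 8.9 g arms, and a common-slope ANCOVA would capture less of it. R² in the table should therefore be read as the variance the fitted model actually removes. The break-even is low enough that the advice hardly depends on it.

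A reader might infer more than the documents support:

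- *That chance size imbalance swamps the H2 contrast.* Table 1 gives 8.9 against 8.4 g EAA, a ratio of 1.06. With an assumed size CV of 15%, the standard error of the difference in mean size between two arms of 8 is 15% × √(2/8) = 7.5%. That ignores the sex stratification. If sex explains half of size variance, the figure is 7.5% × √0.5 = 5.3% (6.3% to 4.1% if sex explains 30% to 70%). Even perfect size adjustment, with an assumed remaining CV of 15% to 25%, leaves a standard error of 7.5% to 12.5%, so adjustment would not make a 6% contrast detectable. Section 1.2 also rests H2 on EAA profile and speed of absorption, not on grams alone.
- *That omitting size equals losing a definite share of subjects.* Any such figure needs CVs and a dose-to-size law that the documents do not contain.
- *That the same argument covers insulin.* Insulin is not an ingested dose, so dilution of a fixed portion does not apply, and it is not named in H1 or H2.

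**Conclusion.** The point holds as a matter of efficiency, not validity. Section 7.1 leaves sex and body size out of the plasma EAA AUC comparison although both are known before the meal and the dose is not scaled to size. On the protocol's own power method, the planned ANOVA has 49% power at f = 0.484, against 53% to 80% with one covariate of assumed R² 0.1 to 0.5. The corresponding detectable f is 0.682, against 0.649 to 0.484. The assumptions are that f = 0.484 is a fair yardstick for this endpoint and that body size or sex explains at least 1% to 2% of its variance. The first matters less for H1, where the EAA doses differ 8.9/4.2 = 2.1-fold and the effect may be well above that value. The documents do not support a claim of bias, of inflated type I error or of any threat to the primary outcome. This is a worthwhile, inexpensive change to a secondary analysis.

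**What to change.** In Section 7.1, before any data are analysed, replace the one-way ANOVA for plasma EAA AUC with a prespecified ANCOVA containing group, sex (the randomization stratum) and one body-size covariate. Choose body weight or DEXA lean mass in advance and use the same one for all subjects. Substituting weight where a DEXA result is missing would put two scales in one covariate. Keep the Bonferroni-adjusted pairwise comparisons, and report the unadjusted ANOVA as a sensitivity analysis.

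The cost is SAP wording and two of 21 residual degrees of freedom (19 remain). No new measurement or visit is needed.

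Do not add mean fasting concentration over 120 to 240 min as a further covariate on this ground. It is a separate question, and the Section 3.1 schedule lists a study supplement at 120 min and the study food at 240 min. Those entries must be reconciled before that window can be treated as fasting.
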